The therapy pod is powered by a Lithium-Ion battery that provides 30-40 hours of therapy (4-7 days of typical use) if fully charged. The battery can be recharged in 2-3 hours by plugging the device into an AC adapter.

3. Study Design

The study is a single site, double blinded, placebo controlled randomized clinical trial. 40 subjects will be selected based on the inclusion criteria stated below and then randomized to either the intervention group or the placebo control group. Prior to the start of this study, a Controlled Substance Utilization Review and Evaluation (CURES) reports will be acquired to establish baseline number of opioid prescriptions for each subject. Subjects will track how consistently they are using pain medications, both opioids and non-opioids, during the two weeks prior to the start of the study. They will also provide twice daily recordings of their pain intensity via a mobile application. At the end of this two-week period, each subject will be fitted with a Quell or a sham device, including initial calibration to the subject's comfort level as described in the background section.

The sham device is identical to Quell in all aspects with one exception. While Quell delivers 1 hour of continuous stimulation during a therapy session, the sham device delivers three 2-minute periods of stimulation at 0, 28 and 58 minutes within the therapeutic session. This limited stimulation should have little to no analgesic effect but should suggest to the subject that they are receiving therapy.

Neither the principal investigator, nor the co-investigator or the subject will know if they are given a sham device or the actual Quell device. The study coordinators will be the only ones who will be aware of which intervention subjects receive. At the end of the study, subjects will be asked if they thought they had the sham or actual device. Both the principal and the co-investigator will be asked to identify which subjects they thought had Quell vs the sham device, prior to analysis of the data.

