Once the study subjects have started using the device, we will also be able to monitor and track their sleep wirelessly via the mobile application as long as they are wearing the device. Subjects will receive weekly check in's to monitor the functionality of the device and to help troubleshoot any issues with the device for the duration of subject participation in the study. These check-ins will take place in person, by phone, and or per subject's usual outpatient oncology visits. Each subject will use their device for 8 weeks, during which they will continue to track their pain, sleep and frequency of pain medication use as stated above. Study investigators will receive automated alerts via email to ensure that study are participants using their devices and that the devices are powered on at regular intervals for the duration of the study.

Both Quell and the sham device communicate via Bluetooth with the same mobile application. This application provides the subjects with a dashboard of device information, trending data on device usage, and sleep quality. This same information will be synced to a cloud so that investigators involved in the study can collect this data remotely, as well as monitor adherence with the device.

Total duration of subject participation will be 10 weeks.

4. Criteria for Evaluation

Primary Efficacy Endpoint

The primary endpoint is a reduction in daily opioid use assessed at weeks 2, 4, 6, 8 and 10 of the study as recorded by the subject in their analgesia diary. This diary will be a preformatted paper form given to each subject at the start of the study, and will include the name and dosage of all the analgesic pain medications prescribed to the subject, as well as any over the counter pain medications the subject will be using. The subjects will be asked to log what times they take their pain medication each day. This diary will then be reviewed and logged into our secure database at each of the clinic visits as stated above. Per previous studies with a similar design, a 20-30% change in opioid consumption is clinically relevant. This end point is chosen as the overall goal of this study is to provide a novel way for patients with cancer to have optimal pain control while reducing their overall opioid use.

Secondary Endpoints

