8.7 Early Withdrawal Visit

- 1. Record any Adverse Experiences/troubleshoot any questions or concerns
- 2. Record changes to concomitant medications.
- 3. Review mobile application for adherence of use.
- 4. Perform and record vital signs.
- 5. Review Mobile Application Pain and Sleep assessment.
- 6. Review documentation of analgesic medication use.
- 7. Perform and record SF-MPQ-2 and Quality of life survey
- 8. Collect Quell/Sham device and delete mobile application from subject's phone
- 9. Administer the PGIC.
- 10. Provide subject with results of any preliminary data analysis pertinent to their involvement in the study.
- 11. Address any remaining question or concerns regarding subject's participation in the study.

9. Data Storage

All data will be transmitted and stored to HIPAA compliant encrypted standards.

Future research:

Subject information will be kept for at least 2 years after completion of this study and up to 20 years for future research that has not yet been planned. Future research using the data will first be approved by Scripps IRB. After 2031, the code that links the sample to the subject's traditionally-identifying information will be destroyed. Related de-identified health information will be kept indefinitely for future research studies at Scripps in secure databases.

10. Statistical Analysis

A biostatistician will perform all data analysis. The sample size (20 participants per group) achieves 80% power to find a 20% (absolute) difference in mean percent change in opioid consumption between the two groups with an estimated standard deviation of mean percent change of 22% and 90% power with an estimated standard deviation of 19% in both groups using a two-sided two-sample t-test with a significance level (alpha) of 0.05.

Descriptive statistics will be calculated for baseline characteristics of both study groups and to assess the effectiveness of the randomization. Repeated measures analysis will be used to assess changes in opioid medication use, pain assessments, and quality of life mesaures over time in the intervention group compared to the control group. Mid study analysis will be conducted with all data amassed around week 6 of all subjects enrolled.

11. Discontinuation and Replacement of Study Participants

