11.1 Early Discontinuation of Quell/Sham Device

A subject may be discontinued from study treatment at any time if the subject, the investigator, or the Sponsor feels that it is not in the subject's best interest to continue. The following is a list of possible reasons for study treatment discontinuation:

- Subject withdrawal of consent (or assent)
- Subject is not compliant with study procedures
- Adverse event that in the opinion of the investigator would be in the best interest of the subject to discontinue study treatment
- Protocol violation requiring discontinuation of study treatment
- Lost to follow-up
- Sponsor request for early termination of study

If a subject is withdrawn from treatment due to an adverse event, the subject will be followed and treated by the Investigator until the abnormal parameter or symptom has resolved or stabilized.

All subjects who discontinue study treatment should come in for an early discontinuation visit as soon as possible and then should be encouraged to complete all remaining scheduled visits and procedures.

All subjects are free to withdraw from participation at any time, for any reason, specified or unspecified, and without prejudice. Reasonable attempts will be made by the investigator to provide a reason for subject withdrawals. The reason for the subject's withdrawal from the study will be specified in the subject's source documents.

Reasonable attempts will be made by the investigator to provide a reason for subject withdrawals. The reason for the subject's withdrawal from the study will be specified in the subject's source documents. As noted above, subjects who discontinue study treatment early (i.e., they withdraw prior to Visit 6) should have an early discontinuation visit. Refer to Section 8 for early termination visit. Subjects who withdraw after Visit 4 but prior to Visit 6 should be encouraged to come in for a final visit (and the procedures to be followed would include those for their next scheduled visit).

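### Does the one-sentence mid-study analysis in protocol section 10 put the type I error, the investigators' arm guess or later self-reports at risk?

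*Protocol*

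**What the plan says.** **Protocol section 10 (Statistical Analysis).** "A biostatistician will perform all data analysis". The section then gives the sample size for one two-sided two-sample t-test at 0.05 and describes a repeated measures comparison of the two arms. It closes with "Mid study analysis will be conducted with all data amassed around week 6 of all subjects enrolled". It names no endpoint, boundary, recipient or decision for that look. SAP section 2.5 does not mention the look.

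**Protocol section 3 (Study Design).** Only the coordinators know the assignments. At the end of the study "subjects will be asked if they thought they had the sham or actual device". Both investigators will be "asked to identify which subjects they thought had Quell vs the sham device, prior to analysis of the data". Section 3 also describes what subjects see of their own data: "This application provides the subjects with a dashboard of device information, trending data on device usage, and sleep quality".

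**Protocol sections 8.6 and 8.7, step 10.** Both have the same instruction: "Provide subject with results of any preliminary data analysis pertinent to their involvement in the study".

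**Protocol section 11.1.** Subjects who stop treatment come for an early discontinuation visit and then "should be encouraged to complete all remaining scheduled visits and procedures". A more specific sentence covers late withdrawals: "Subjects who withdraw after Visit 4 but prior to Visit 6 should be encouraged to come in for a final visit". A parenthesis adds that the procedures include those of the next scheduled visit.

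**The concern.** The look is announced directly after a between-arm comparison, so a by-arm efficacy analysis is a natural reading. Section 19 says there is no Data Safety Monitoring Board, and section 11.1 lists early termination at the sponsor's request without criteria. A reader may reasonably ask three things.

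- Is this a second test at 0.05? If so, the overall error rate would exceed 5%.
- Do the investigators guess each subject's device before or after this look? A guess made after by-arm results are seen is a weaker check of the blind.
- Does step 10 of 8.7 pass mid-study results to subjects who then keep attending? The primary endpoint is a self-completed diary and the main secondary endpoints are self-reports, so a change in expectation could carry into later data.

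**Working it through.** **1. The plan's own figure.** Inputs from protocol section 10: 20 per arm, difference 20, SD 22 or 19, two-sided alpha 0.05. The noncentrality is 20 / (SD × √(2/20)), with 38 degrees of freedom.

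- SD 22: 20 / 6.957 = 2.875, power 80.0%.
- SD 19: 20 / 6.008 = 3.329, power 90.0%.

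Both protocol figures reproduce with a single test at the full 0.05. The design gives no alpha to the mid-study look, which fits a look that is not a test. (The SAP pairs the two powers with the SDs the other way round. That is a separate matter.)

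**2. Type I error if the look were a test.** Assume both looks are tested by arm at 0.05 and either can support a claim. Overall error is 1 − P(|Z1| < 1.960 and |Z2| < 1.960), with the statistics bivariate normal with correlation ρ. The documents do not give ρ.

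| ρ (assumed) | overall error |
|---|---|
| 0.5 | 9.07% |
| 0.7 | 8.35% |
| 0.8 | 7.81% |
| 0.9 | 7.04% |

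The documents state none of these conditions. If the look is pooled, or by arm but unable to support a claim, the error stays at 5%.

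**3. How many subjects could still be influenced.** Take the look as a single analysis when the last enrollee reaches week 6. A subject enrolled d weeks earlier is then at week 6 + d.

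- d < 2: two primary assessments remain (weeks 8 and 10).
- 2 ≤ d < 4: one remains.
- d ≥ 4: none remains.

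Only subjects enrolled in the last 4 weeks matter. With 40 subjects enrolled evenly over W weeks (assumed), that is 40 × 4 / W:

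- W = 26: 6.2
- W = 52: 3.1
- W = 104: 1.5

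Only those who stop early after the look can meet step 10 of 8.7 and still have visits ahead. They have about 2 weeks left on average. Assume a constant dropout rate over the 8 device weeks:

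- 20% dropout: 1 − 0.8^(2/8) = 5.4%. Times 6.2, 3.1 and 1.5, this is about 0.3, 0.2 and 0.1 subjects.
- 40% dropout: 1 − 0.6^(2/8) = 12.0%. This is about 0.7, 0.4 and 0.2 subjects.

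**4. What happens to such a subject.** At the look, everyone still in follow-up is at or past week 6, so a later withdrawal falls between Visit 4 and Visit 6. Section 11.1's specific sentence points to a final visit with the next visit's procedures.

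- Next visit is Visit 5 (section 8.5): a phone review of analgesic use or, in clinic, the Visit 3 list. Neither has a results step.
- Next visit is Visit 6 (section 8.6): the diary review, SF-MPQ-2 and quality of life come before step 10, as do PGIC and the sleep scale. No visit follows.
- The 8.7 list is used: the diary review, SF-MPQ-2, quality of life and PGIC precede step 10. The device is collected and the app deleted at step 8, so no app data follow.

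**5. The investigators' guess.** Section 3's phrase has two readings.

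- Literal: the guess precedes any analysis, including the mid-study one. The cost is that investigators guess before the last visits of the few subjects counted in step 3.
- End of study: the guess follows the look. This matters only if by-arm results went to the investigators, and no passage sends them there.

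The guess is a check on the blind, not an endpoint, and neither section 10 nor SAP section 2.5 specifies an analysis of it.

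**The case for a change.** The strongest reply is that silence is not protection. Nothing forbids a by-arm look, nothing bars the investigators from seeing it, and step 10 is not expressly confined to the subject's own data. On the end-of-study reading, the arm guess for all 40 subjects could follow a look whose results were known. Section 11.1's general sentence, encouraging all remaining visits, overlaps with the final-visit rule, and the parenthesis says only that the procedures include those of the next visit. So the 8.7 route is narrow but not shut.

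That much stands: the text could be clearer in sections 3 and 10. The rest is weaker. The protocol never calls the mid-study analysis preliminary, so the link to step 10 is an inference. Step 10 is qualified by relevance to the subject's own participation, and steps 3, 5 and 6 of the same visit review that subject's own records. By-arm means do not reveal anyone's assignment, and the coordinators know the assignments already. Splitting alpha as 0.001 and 0.049 would gain nothing if the biostatistician alone held the result, because nobody could act on it.

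**Conclusion.** No change to the plan follows. The gap is real, but it is one of detail. Followed as written, the look triggers no claim and no stopping rule, the final test is the only one at 0.05, and the investigators guess before the data are analysed. The 7.0% to 9.1% range describes a procedure the documents do not set out. Expected exposure through the early-withdrawal visit is below one subject in every case computed (about 0.1 to 0.7), and the questionnaires listed for that visit are completed before any results are given.

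This rests on four assumptions: one look when the last enrollee reaches week 6; even accrual over 26 to 104 weeks; 20% to 40% dropout over the device period; and a biostatistician who does not release by-arm results while subjects are still being followed. A rolling look, or a by-arm test able to end the trial or support a claim, would reopen the question. No passage describes either.

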11.1 Early Discontinuation of Quell/Sham Device

A subject may be discontinued from study treatment at any time if the subject, the investigator, or the Sponsor feels that it is not in the subject's best interest to continue. The following is a list of possible reasons for study treatment discontinuation:

- Subject withdrawal of consent (or assent)
- Subject is not compliant with study procedures
- Adverse event that in the opinion of the investigator would be in the best interest of the subject to discontinue study treatment
- Protocol violation requiring discontinuation of study treatment
- Lost to follow-up
- Sponsor request for early termination of study

If a subject is withdrawn from treatment due to an adverse event, the subject will be followed and treated by the Investigator until the abnormal parameter or symptom has resolved or stabilized.

All subjects who discontinue study treatment should come in for an early discontinuation visit as soon as possible and then should be encouraged to complete all remaining scheduled visits and procedures.

All subjects are free to withdraw from participation at any time, for any reason, specified or unspecified, and without prejudice. Reasonable attempts will be made by the investigator to provide a reason for subject withdrawals. The reason for the subject's withdrawal from the study will be specified in the subject's source documents.

Reasonable attempts will be made by the investigator to provide a reason for subject withdrawals. The reason for the subject's withdrawal from the study will be specified in the subject's source documents. As noted above, subjects who discontinue study treatment early (i.e., they withdraw prior to Visit 6) should have an early discontinuation visit. Refer to Section 8 for early termination visit. Subjects who withdraw after Visit 4 but prior to Visit 6 should be encouraged to come in for a final visit (and the procedures to be followed would include those for their next scheduled visit).

11.2 Replacement of Subjects

Subjects who withdraw from the study treatment will not be replaced, as long some data has been collected from the device. This withdraw will be accounted for in our data analysis. Should subjects withdraw from the study without ever using the device, their device will be collected and they will be replaced with a new participant.

11.3 Protocol Violations

A protocol violation occurs when the subject, investigator, or Sponsor fails to adhere to significant protocol requirements affecting the inclusion, exclusion, subject safety and primary endpoint criteria. Protocol violations for this study include, but are not limited to, the following:

- Failure to meet inclusion/exclusion criteria
- Use of a prohibited concomitant medication

• Include other specific examples as appropriate for the study (non-adherence with study drug regimen, etc.)

Failure to comply with Good Clinical Practice (GCP) guidelines will also result in a protocol violation. The Sponsor will determine if a protocol violation will result in withdrawal of a subject.

When a protocol violation occurs, it will be discussed with the investigator and a Protocol Violation Form detailing the violation will be generated. This form will be signed by a Sponsor representative and the Investigator. A copy of the form will be filed in the site's regulatory binder and in the Sponsor's files.

12. Potential Risks

Risk from the device:

Transcutaneous electrical nerve stimulation therapy is considered mostly safe. On rare occasions, an electrical current will be too intense for a subject, causing irritation on the skin. On very rare cases, some subjects have reported some calf muscle cramping with prolonged use.

Some subjects with skin allergies may react to the electrode pads used with the units. People with pacemakers, infusion pumps, defibrillators, and similar devices should not be exposed to the electrical currents produced by transcutaneous electrical nerve stimulation.

Psychological or Social Risks Associated with Loss of Privacy:

In spite of all the safety measures that we will use, we cannot guarantee that the subject's identity will never become known. Every effort will be made to secure the information stored on the mobile application and the information uploaded into the cloud database. In order to maintain subject confidentiality, only a site number, subject number and subject initials will identify all study subjects on any documentation submitted to the Sponsor.

13. Potential Benefits

Subjects enrolled in this study have the potential to have their pain adequately managed while down titrating their overall opioid use. There may be no direct benefit to the subject

for participating in this study. Knowledge gained by conducting this study may lead to the identification of mechanisms that may lead to improved detection and treatment of subjects with cancer related pain.

14. Risk-Benefit Ratio

There is minimal risk of physical harm with any of the devices used. As with any electronic means of communication, no matter how secure, there is always a risk of a data breach.

15. Alternative Treatment(s)

This study involves the addition of a drug free wearable pain device. Subjects may refuse participation in this study and this will not influence their care in any way.

16. Subject Payment/Costs

Subjects will be paid per study visit. Additionally, should they choose, they can keep the Quell device as well as 6 months worth of electrodes. Subjects who were assigned the sham device will be given the option of using and keeping the Quell device.

17. Informed Consent

Informed consent will be obtained in accordance with the Declaration of Helsinki, ICH GCP, US Code of Federal Regulations for Protection of Human Subjects (21 CFR 50.25[a,b], CFR 50.27, and CFR Part 56, Subpart A), the Health Insurance Portability and Accountability Act (HIPAA, if applicable), and local regulations.

The Investigator will prepare the informed consent form, assent and HIPAA authorization and provide the documents to the Sponsor or designee for approval prior to submission to the IRB.

The consent form generated by the Investigator must be acceptable to the Sponsor and be approved by the IRB.

The study personnel that have been trained on this study protocol by the sponsor (investigator, designated co-investigator or research coordinator) will obtain informed consent for this study. Subjects will be given ample time to read and understand the consent form in their native language. Subjects will have an opportunity to ask the investigator and or coordinator questions and have all questions answered before signing. Once the subject has signed the informed consent, a copy will be given to them. The original consent will be filed at the study site.

18. Confidentiality of Data/Privacy of Individuals

Scripps Translational Science Institute affirms the subject's right to protection against invasion of privacy. Data files are stored on a password-protected computer/database and will be accessible only to the above listed investigators and research staff. Subject's data

will be assigned and identified by a unique code. Traditional identifying information such as name, address, phone, medical record number, etc will not be included in the database. Only the investigators and the research staff will have the link that can match the code to identifying information. Study files will be kept in secure locations at each study site.

19. Safety

Adverse Events:

Any event that occurs during the study period and is considered to be directly related to the study procedures will be considered an adverse event. All possible events will be reported to Scripps Translational Science Institute. Loss of privacy would also be considered a reportable adverse event.

Serious Adverse Events:

We do not anticipate any serious adverse events related to this study. However, events that fit the definition of a serious adverse event according to ICH guidelines must be reported to STSI within 24 hours.

Such events include any untoward medical occurrence that is life threatening, results in death, requires hospitalization or prolongation of existing hospitalization, and/or results in persistent or significant disability/incapacity. Medical Events that may not be immediately life threatening or result in death or hospitalization should also be considered serious when they jeopardize the subject or require intervention to prevent one of the other outcomes listed in the serious definition.

The study Principal Investigator at Scripps will review adverse events and serious adverse events directly related to loss of privacy. This study does not have a Data Safety Monitoring Board.

20. Monitoring

STSI will monitor the study throughout its duration. The study monitor will visit the site at appropriate intervals to review investigational data for accuracy and completeness and to ensure adherence with the protocol. The investigator/site will permit access to all documents and records maintained on the subjects in the study. Source documents will be reviewed to ensure all subjects have properly signed and dated the informed consent/HIPAA forms. All information will be reviewed to ensure eligibility criteria as per the protocol, and supporting source data will be verified. The Investigator and/or research coordinator must be available for monitoring visits. STSI will collect the appropriate regulatory document records at the site will also be reviewed periodically during monitoring visits for accuracy and completeness.

*Enrollment may not begin at the study site until all required documentation is collected, key study personnel are trained and written approval from STSI is given to start enrollment.

21. Record Retention

Research records will be kept for at least 2 years after study completion. Scripps will continue to store and use the subject information for up to 20 years. In 2031, the code that links the subject to the identifying health and trait information will be destroyed. The data and related de-identified health and trait information may be kept indefinitely. Record retention must also comply with any specific requirements of the local reviewing IRB. (i.e. Scripps- must keep HIPAA form for at least 6 years after study completion)

Records will ultimately be kept at the research site until STSI has given written permission to destroy the records. If record retention cannot be maintained by the participating sites, STSI must be notified and storage will be provided.

22. Publication

The preparation and submittal for publication of manuscripts containing the study results shall be in accordance with a process determined by mutual written agreement among the study Sponsor and participating institutions. The publication or presentation of any study results shall comply with all applicable privacy laws, including, but not limited to, the Health Insurance Portability and Accountability Act of 1996.

23. Facilities and Personnel

Site Selection

Investigators and participating centers will be selected at institutions with access to an established IRB or equivalent that meets on a regular basis. An interest in participating in the study and willingness to support monitoring and auditing procedures will be prerequisites. Other considerations include the center's ability to execute the study protocol and a prospective subject population that will meet the protocol criteria.

Clinical Trial Agreement

A Clinical Trial Agreement must be signed by all parties named in the Clinical Trial Agreement and returned to Scripps Translational Science Institute prior to the commencement of any study activities.

Personnel Training

